5.5.3 Laboratory Assessments

Testosterone and PSA levels will be assessed for all patients at each scheduled visit, prior to administering ELIGARD[®], and at the follow up visit. Information on other laboratory tests will only be collected if the tests are done within routine clinical practice. The laboratory tests include lactate dehydrogenase (LDH), alkaline phosphatase (ALP), hematology, LFT and RFT.

5.5.4 Imaging

Data on tumor evaluation/ radiographic assessments will only be collected if available. Radiographic evaluation includes computerized tomography (CT) scan, positron emission tomography (PET) scan, magnetic resonance imaging (MRI), Bone scan, X-ray, ultrasound or any other imaging test which have been performed as part of standard of care.

5.6 Adverse Events and Other Safety Aspects

AE and SAE collection will start from signing of informed consent form (ICF) until the follow-up visit at 18 months, or early withdrawal/discontinuation.

5.6.1 Definition of Adverse Events (AEs)

An AE is defined as any untoward medical occurrence in a patient administered a study drug or has undergone study procedures and which does not necessarily have a causal relationship with this treatment. An AE can therefore be any unintended sign (including an abnormal laboratory finding), symptom, or disease temporally associated with the use of a medicinal (investigational) product, whether or not related to the medicinal (investigational) product.

An abnormality identified during a medical test (e.g., laboratory parameter, vital sign, electrocardiogram [ECG] data, physical exam) should be defined as an AE only if the abnormality meets 1 of the following criteria:

- Induces clinical signs or symptoms
- Requires active intervention
- Requires interruption or discontinuation of study medication
- The abnormality or investigational value is clinically significant in the opinion of the investigator.

5.6.2 Definition of Serious Adverse Events (SAEs)

An adverse event will be considered to be “serious” if, in the view of either the investigator or Sponsor, it results in any of the following outcomes:

- Results in death
- Is life threatening (an AE is considered “life-threatening” if, in the view of either the investigator or Sponsor, its occurrence places the patient at immediate risk of death. It does not include an AE that, had it occurred in a more severe form, might have caused death)
- Results in persistent or significant disability/incapacity or substantial disruption of the ability to conduct normal life functions
- Results in congenital anomaly, or birth defect
- Requires inpatient hospitalization or leads to prolongation of hospitalization (hospitalization for treatment/observation/examination caused by AE is to be considered as serious)
- Other medically important events

Medical and scientific judgment should be exercised in deciding whether expedited reporting is appropriate in other situations, such as important medical events that may not be immediately life-threatening or result in death or hospitalization, but may jeopardize the patient or may require intervention to prevent 1 of the other outcomes listed in the definition above. These events,

including those that may result in disability/incapacity, should also usually be considered serious. Examples of such events are intensive treatment in an emergency room or at home for allergic bronchospasm, blood dyscrasias or convulsions that do not result in hospitalization; or development of drug dependency or drug abuse.

Safety events of interest on the medicinal products administered to the patient as part of the study (e.g., study drug, comparator, and background therapy) that may require expedited reporting and/or safety evaluation include, but are not limited to:

- Overdose of the medicinal product(s)
- Suspected abuse/misuse of the medicinal product(s)
- Inadvertent or accidental exposure to the medicinal product(s)
- Medication error involving the medicinal product(s) (with or without subject/patient exposure to the Sponsor medicinal product, e.g., name confusion)

All of the events of interest noted above should be recorded on the eCRF. Any situation involving these events of interest that also meets the criteria for an SAE should be recorded on the AE page of the eCRF and marked 'serious' and on SAE worksheet. Refer to Section 5.6.5 below for SAE reporting timeline and procedure.

The Sponsor has a list of events that they classify as "always serious" events (refer to the Appendix). If an AE is reported that is considered to be an event per this classification as "always serious", additional information on the event may be requested.

5.6.3 Criteria for Causal Relationship to the Study Drug

AEs that fall under either "Possible" or "Probable" should be defined as "AEs whose relationship to the study drugs could not be ruled out";

Causal relationship to the study drug	Criteria for causal relationship
Not Related	A clinical event, including laboratory test abnormality, with a temporal relationship to drug administration which makes a causal relationship improbable, and/or in which other drugs, chemicals or underlying disease provide plausible explanations.
Possible	A clinical event, including laboratory test abnormality, with a reasonable time sequence to administration of the drug, but which could also be explained by concurrent disease or other drugs or chemicals. Information on drug withdrawal may be lacking or unclear.

Probable	A clinical event, including laboratory test abnormality, with a reasonable time sequence to administration of the drug, unlikely to be attributed to concurrent disease or other drugs or chemicals, and which follows a clinically reasonable response on re-administration (rechallenge) or withdrawal (dechallenge).
-----------------	---

For this study, an ELIGARD[®]-related AE is defined as an adverse event in a patient administered ELIGARD[®] where a causal relationship is at least a reasonable possibility (drug event with either a possible or probable causal relationship), as determined by the investigator. Adverse events listed in the local label should be used by the investigator as reference safety information to understand whether an adverse event is expected with the use of ELIGARD[®]. This understanding should inform their causality assessments.

5.6.4 Criteria for Defining the Severity of an Adverse Event

AEs, including abnormal clinical laboratory values, will be graded using the National Cancer Institute (NCI)-Common Terminology Criteria for Adverse Event (CTCAE) guidelines (Version 4.03). The items that are not stipulated in the NCI-CTCAE Version 4.03 will be assessed according to the criteria below and entered into the eCRF:

Grade	Assessment Standard
1-Mild	Asymptomatic, or mild symptoms, clinical or diagnostic observations noted; intervention not indicated.
2-Moderate	Local or noninvasive intervention indicated.
3-Severe	Medically significant but not immediately life threatening, hospitalization or prolonged hospitalization.
4-Life Threatening	Life threatening consequences, urgent intervention indicated
5-Death	Death related to AE

5.6.5 Reporting of Serious Adverse Events (SAEs)

In the case of an SAE, the investigator should complete and submit an SAE Worksheet in the eCRF containing all information that is required by the Regulatory Authorities to the Sponsor/contract research organization (CRO) within 24 hours of awareness following the procedure outlined in the Safety Reporting Guide provided to the sites. AEs should be reviewed

by Investigator in a timely fashion, i.e., if an AE is upgraded to an SAE, these need to be reported to the Sponsor /delegated designee within 24 hours. If completion of the SAE worksheet is not possible through the eCRF, email or by fax within 24 hours, the Sponsor's local drug safety contact/ CRO should be informed by phone.

For contact details, see **Section II Contact Details of Key Sponsor's Personnel**.

If there are any questions, or if clarification is needed regarding the SAE, please contact the Sponsor's Medical Monitor or his/her designee (see **Section II Contact Details of Key Sponsor's Personnel**).

Follow-up information for the event should be sent promptly (within 7 days of the initial notification).

Full details of the SAE should be recorded on the medical records and on the eCRF.

The following minimum information is required:

- ISN/Study number,
- Patient number, sex and age,
- The date of report,
- A description of the SAE (event, seriousness of the event), and
- Causal relationship to the study drug.

The Sponsor or Sponsor's designee will submit expedited safety reports to the regulatory agencies in accordance to the local regulations, and will inform the investigators of such regulatory reports. Investigators must submit safety reports as required by their IRB/IEC within timelines set by regional regulations. Documentation of the submission to and receipt by the IRB/IEC of expedited safety reports should be retained by the site. The investigators should provide written documentation of IRB/IEC notification for each report to the Sponsor.

Investigators may contact the Sponsor's Medical Monitor for any other problem related to the safety, welfare, or rights of the patient.

Reporting of SAEs in case of ELIGARD[®] treatment discontinuation

For patients who discontinue ELIGARD[®] treatment, AE monitoring should be continued for a period of 3 months from the date of last administration of ELIGARD[®], provided consent is not withdrawn. AE documentation and SAEs reporting should be continued during this period of time. SAEs that are considered to be related to ELIGARD[®] occurring after the end of the observation period or after end of the follow-up period should be reported according to local law/guidelines within the spontaneous reporting system.

Safety Observations

The investigator should take all appropriate measures to ensure the safety of the patients. The outcome of all reported SAEs (e.g., resolution, death) will be followed up and documented. Reporting to the relevant Regulatory Authorities according to national regulations will be done by the Sponsor.

5.6.6 Follow-up of Adverse Events

All AEs occurring during or after the patient has discontinued the study are to be followed-up until resolved or judged to be no longer clinically significant, or until they become chronic to the extent that they can be fully characterized.

If during AE follow-up, the AE progresses to an "SAE", or if a patient experiences a new SAE, the investigator must immediately report the information to the Sponsor.

Please refer to **Appendix 12.3 Liver Safety Monitoring and Assessment** for detailed instructions on Drug Induced Liver Injury (DILI).

5.6.7 Monitoring of Common Serious Adverse Events

Common SAEs are SAEs commonly anticipated to occur in the study population independent of drug exposure. SAEs classified as "common" are provided in **Appendix 12.4 Common Serious Adverse Events** for your reference. The list does NOT change your reporting obligations or prevent the need to report an AE meeting the definition of an SAE as detailed above. The purpose of this list is to alert you that some events reported as SAEs may not require expedited reporting to the regulatory authorities based on the classification of "common serious adverse events" as specified in **Appendix 12.4 Common Serious Adverse Events**. The Sponsor will monitor these events throughout the course of the study for any change in frequency. Any changes to this list will be communicated to the participating investigational sites. Investigators must report individual occurrences of these events as stated in **Section 5.6.5 Reporting of Serious Adverse Events**.

5.6.8 Procedure in Case of Pregnancy of Partner

This study involves male prostate cancer patient. If a partner of a male patient becomes pregnant during the study while taking the medication the investigator should report the information to the Sponsor/delegated designee within 24 hours of awareness as if it is an SAE. The expected date of delivery or expected date of the end of the pregnancy of partner, paternal drug exposure etc., should be included in this information. If limited data are reported, reasonable effort should be made to complete these.

The investigator will follow the medical status of the mother, as well as the fetus, as if the pregnancy is an SAE and will report the outcome to the Sponsor.

When the outcome of the pregnancy falls under the criteria for SAEs (spontaneous abortion, induced abortion, stillbirth, death of newborn, congenital anomaly [including anomaly in a miscarried fetus]), the investigator should respond in accordance with the report procedure for SAEs. Additional information regarding the outcome of a pregnancy (which is categorized as an SAE) is mentioned below.

- "Spontaneous abortion" includes miscarriage, abortion and missed abortion
- Death of an infant within 1 month after birth should be reported as an SAE regardless of its relationship with the study drug
- If an infant dies more than 1 month after the birth, it should be reported if a relationship between the death and intrauterine exposure to the study drug is judged as "possible" by the investigator
- In the case of a delivery of a living newborn, the "normality" of the infant is evaluated at the birth
- Unless a congenital anomaly are identified prior to spontaneous abortion or miscarriage, the embryo or fetus should be assessed for congenital defects by visual examination

5.6.9 Emergency Procedures and Management of Overdose

In the event of suspected overdose, refer to the approved Package Insert or local product information supplied by Astellas.

5.6.10 Supply of New Information Affecting the Conduct of the Study

When new information becomes available necessary for conducting the clinical study properly, the Sponsor will inform all investigators involved in the clinical study as well as the regulatory authorities. Investigators should inform the IRB/IEC of such information when needed.

5.7 Test Drug Concentration

Not applicable.

5.8 Other Measurements, Assessments or Methods

5.8.1 Prostate Cancer Status

Information on prostate cancer status will be collected at the baseline visit and each follow-up visit. The information will include stage of prostate cancer, bone metastasis, soft tissue disease, visceral disease, pain (using VAS 0-10), and ECOG status.

5.8.2 Supportive Care

Information on other supportive care treatment will be collected at the baseline visit and each follow-up visit, and will be recorded in the eCRF. The information will include type of

treatment, drug dose, schedule and duration, supportive care measures, other concomitant medications related to cancer (e.g., pain medications, bone protective medications, spinal cord decompression surgery, palliative radiotherapy)

5.8.3 Concomitant Medications Assessment

Information on concomitant medication will be collected at the baseline visit and each follow-up visit, and will be recorded in the eCRF. The information will include generic or brand names of the medication, the dose, unit, route, frequency, start and end dates and the reason for taking the medication.

5.9 Total Amount of Blood

The total volume of blood to be drawn is 35 ml during the entire study (from baseline to follow-up visit) with 5 ml per visit.

6 DISCONTINUATION

6.1 Discontinuation of Individual Patients

A discontinuation is a patient who enrolled in the study and for whom study treatment is permanently discontinued prematurely for any reason.

A patient is free to withdraw from the study for any reason, at any time, without reason for doing so and without penalty or prejudice.

A patient will be discontinued from the study in the case of:

1. Withdrawal of consent - patient decision to withdraw from further participation in the study
2. Patient safety is at risk (at the discretion of the treating physician)
3. Patient develops CRPC as determined by European Association of Urology (EAU) Prostate Cancer Guidelines 2016
4. Patient is lost to follow-up
5. Patient death during the study
6. Patient misses consecutive visit periods (window \pm 14 days) during the study
7. Patient who is less than 80% compliant with the dosage regimen for any 2 consecutive visit periods (window \pm 14 days) during the study.
8. Site terminated by the Sponsor
9. Study terminated by the Sponsor
10. Cessation of treatment with ELIGARD[®] (at the discretion of the treating physician). The reasons for stopping treatment will be noted (e.g., PSA progression, radiographic progression, clinical progression, AE, drug administration issues, other).
11. Patient takes prohibited medications as described in Section 5.1.6 and Section 12.2

For patients that discontinue from the study, the reason for discontinuation should be recorded in the eCRF. Patients that discontinue will have an Early Withdrawal visit 3 months after the last administration of ELIGARD[®] for safety assessment. At the end of a patient's involvement in this study, the Investigator must ensure that all outstanding data entry is entered in the eCRF unless the patient withdrew consent for their data to be used.

6.2 Discontinuation of the Site

If an investigator intends to discontinue participation in the study, the investigator must immediately inform the Sponsor/delegated designee.

6.3 Discontinuation of the Study

The Sponsor may terminate this study prematurely, either in its entirety or at any study site, for reasonable cause provided that written notice is submitted in advance of the intended termination. Advance notice is not required if the study is stopped due to safety concerns. If the Sponsor terminates the study for safety reasons, the Sponsor will immediately notify the investigator and subsequently provide written instructions for study termination.

7 STATISTICAL METHODOLOGY

Data analysis will be performed by the designated CRO in accordance with the CRO's SOPs for statistics and clinical programming with oversight from MA Statistics of the Sponsor. All study specific processes and definitions will be documented. Data analysis will be performed in adherence to Astellas data standards.

Analyses that will be performed on the primary and secondary variables are described in this section. A more technical and detailed elaboration of the statistical analysis of the primary and secondary variables and other data will be included in a separate Statistical Analysis Plan (SAP) and result tables specification manual. The SAP will be finalized before the database soft lock at the latest. Any changes from the analyses planned in SAP will be justified in the Clinical Study Report.

Summary statistics of all variables (demographic and clinical) will be produced in the form of tables. Descriptive statistics (mean, median, standard deviation [SD], etc.) in addition to graphical representation of the data (plots, histograms, etc.) will be presented. For continuous variables, descriptive statistics will include the number of patients (n), mean (for observed values and absolute changes from baseline), SD, median, minimum and maximum. Two-sided 95% CI will be calculated for mean changes from baseline. For categorical variables, the number and percentage of patients by each category will be tabulated by visit. The number of missing values will be specified for each variable. Cross tabulations will be produced to explore relationships between variables. No formal statistical comparisons will be performed.

7.1 Sample Size

This study targets to enroll approximately 107 prostate cancer patients.

The sample size was calculated based on the estimated percentage of ELIGARD[®]-related AEs, as well as the desired width of its 95% CI. Prior clinical studies on ELIGARD[®] have shown an ELIGARD[®]-related AEs rate of around 50% of patients during a six-month treatment period [ELIGARD Investigator's Brochure, June 2008; Tombal & Berges, 2007]. With the assumption that the percentage of ELIGARD[®]-related AEs will be 50%, a sample size of 96 completed patients is sufficient for estimating a Wald 95% CI with a width of 20% (+/- 10% from the middle), based on a finite population correction, with factor N=10,000.

Therefore, the total sample size of this study, assuming a drop-out rate of 10%, is 107 patients.

PASS 14 Power Analysis and Sample Size Software (2015) version number 14.0.2 was used in the sample size calculation (NCSS, LLC, Kaysville, Utah, USA, ncss.com/software/pass).

7.2 Analysis Set

Detailed criteria for analysis sets will be laid out in Classification Specifications and the allocation of patients to analysis sets will be determined prior to database hard-lock.

7.2.1 Full Analysis Set (FAS)

The full analysis set (FAS) will consist of all patients who are enrolled and receive at least 1 dose of study drug and have at least 1 post baseline measurement of PSA and testosterone levels. This will be the primary analysis set for efficacy analyses.

7.2.2 Per Protocol Set (PPS)

The per protocol set (PPS) will consist of the subset of the FAS who do not meet criteria for PPS exclusion. These criteria are to capture relevant non-adherence to the protocol and are listed below:

- Entered into the study even though they did not satisfy entry criteria
- Developed withdrawal criteria during the study and was not withdrawn (Patients who discontinued the study for efficacy-related reasons, such as insufficient therapeutic effect, will be included in the PPS.)
- Full dose was not administered or drug reconstitution was not performed as prescribed
- Patients with treatment compliance <80%
- Patients who used prohibited concomitant medication as defined in protocol

Further criteria may be defined in the SAP. The PPS will be a secondary analysis set for efficacy analyses. Select demographic and baseline characteristics may also be summarized for the PPS.

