5.1.6 Restrictions During the Study

The following drugs are prohibited to be used throughout the study (*see Section 12.2*):

1. Other LHRH analogues,
2. LHRH antagonists and other agents (approved or investigational) which are known to impact on testosterone or PSA level,
3. Ketoconazole,
4. Estrogens,
5. Herbal medications that may affect PSA levels (i.e., saw palmetto),
6. Androgens (testosterone, dihydroepiandrosterone, etc.),
7. Abiraterone,
8. Enzalutamide,
9. Chemotherapy agents including docetaxel and platinum drugs

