7.4 Analysis of Efficacy

Efficacy analysis will be conducted on the FAS and PPS. The interpretation of results from statistical tests will be based on the FAS. The PPS will be used to assess the robustness of the results from the statistical tests based on the FAS.

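### Section 7.2.2 both includes and excludes a patient who stops for progression and then has a listed drug recorded; the undated exclusion would remove observed progressors from the PPS

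*Protocol*

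**What the plan says.** Protocol section 7.2.2 defines the PPS as the FAS minus patients who meet any of five exclusion criteria, which are meant to capture relevant non-adherence. Two statements in that list matter here.

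- The last criterion excludes "Patients who used prohibited concomitant medication as defined in protocol". It carries no date limit and no exception.
- A parenthesis attached to the second criterion (met a withdrawal criterion but was not withdrawn) says: "Patients who discontinued the study for efficacy-related reasons, such as insufficient therapeutic effect, will be included in the PPS".

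Section 5.1.6 sets the scope of the prohibition: "The following drugs are prohibited to be used throughout the study". Its nine items include abiraterone, enzalutamide, agents known to affect testosterone or PSA, and "Chemotherapy agents including docetaxel and platinum drugs". Section 12.2 repeats the list.

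Section 7.4 gives the PPS its job: "The PPS will be used to assess the robustness of the results from the statistical tests based on the FAS". Section 7.2.1 makes the FAS the primary efficacy set, and the FAS has no medication exclusion.

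**The concern.** A per-protocol set should drop patients for how the protocol was followed, not for how they responded. Some listed drugs could be started because ELIGARD has failed. If such a start removes the patient from the PPS, membership depends in part on the outcome being analysed.

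Time to PSA progression is a named secondary endpoint (section 7.4.2). Losing observed progressors from the PPS would make that result look better than the FAS result. A difference between the two sets could then reflect the membership rule rather than protocol adherence. The sponsor evidently wanted to keep efficacy failures in the PPS, but the text does not secure this.

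**Working it through.** **Is there a plan figure to reproduce?** No. The protocol gives no expected number of PPS exclusions, progression rate or rate of listed-drug use. The sample size in section 7.1 (96 completers, 107 enrolled) does not bear on this point.

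**Can one patient meet both rules?** Setting the sections side by side:

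1. Section 6.1 discontinues a patient for CRPC: "Patient develops CRPC as determined by European Association of Urology (EAU) Prostate Cancer Guidelines 2016". It also names PSA, radiographic and clinical progression among the reasons for stopping ELIGARD. These are efficacy-related reasons, so the inclusion sentence in 7.2.2 covers such a patient.
2. Section 6.1 brings discontinued patients back for an Early Withdrawal visit 3 months after the last dose. Table 1 marks concomitant medications at that visit, and section 5.8.3 records start and end dates. A listed drug started after stopping can therefore enter the database.
3. Section 7.5.1.1 plans separate summaries of related AEs that occur after CRPC management. The protocol thus expects such treatment while patients are under observation.
4. The exclusion in 7.2.2 does not ask when the drug was started, so read literally it removes this patient.
5. Section 6.1 has a further discontinuation reason: "Patient takes prohibited medications as described in Section 5.1.6 and Section 12.2". If a listed drug is added for progression, the failure may be recorded under this reason instead of an efficacy reason. The inclusion sentence might then not reach the patient at all.

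One rule keeps the patient, the other removes him, and no sentence ranks them.

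**Does the exclusion protect the data?** Table 1 marks neither PSA nor testosterone at the Early Withdrawal visit. A drug started after stopping therefore has no scheduled efficacy value to contaminate at that visit. What the exclusion removes is a progression already observed.

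**Direction.** Let p be the FAS proportion with PSA progression and f the share of progressors dropped for listed-drug use. If non-progressors are not dropped for this reason,

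PPS proportion = p(1 − f) / (1 − pf).

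This is below p whenever f > 0 and p < 1. If a share g of non-progressors is also dropped, the PPS proportion is p(1 − f) / [p(1 − f) + (1 − p)(1 − g)], which is below p whenever f > g.

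**Illustration.** All rates are assumed; g = 0.

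| FAS proportion p | f = 25% | f = 50% | f = 75% |
|---|---|---|---|
| 10% | 7.7% | 5.3% | 2.7% |
| 20% | 15.8% | 11.1% | 5.9% |
| 30% | 24.3% | 17.6% | 9.7% |

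For example, p = 20% and f = 50% gives 0.20 × 0.50 / (1 − 0.10) = 0.10 / 0.90 = 11.1%. These are crude proportions standing in for a time-to-event endpoint, so they show direction and possible range only.

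**The case against.** **The exclusion may not have been meant to reach these patients.** Concomitant can be read as during study treatment only. The criteria are meant to capture non-adherence, and a patient withdrawn for CRPC and then treated has followed the protocol. The inclusion sentence itself is unqualified; only its placement ties it to one criterion. This stands as a possible reading. It makes the result an unresolved conflict rather than a certain exclusion, but it does not settle which rule applies.

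**Detail is deferred.** Section 7.2 leaves detailed criteria to the Classification Specifications, and 7.2.2 lets the SAP add criteria. That would answer an omission. Here two stated rules give opposite results for the same patient.

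**Stronger readings that the documents do not support:**

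- *All treatment failures leave the PPS.* Only failures with a recorded listed drug are touched. Section 2.2.1 also says that treatments given after month 15 or the last visit are not collected, which narrows the exposure.
- *The list is mainly post-progression therapy.* Five or six of the nine items could be read that way, but that is a clinical classification the protocol does not make.
- *The testosterone result is also flattered.* The protocol's CRPC definition requires castrate testosterone (below 50 ng/dL), so removing CRPC patients removes men with suppressed levels. The endpoint is at 1 and 1.5 years, when early discontinuers generally have no value in either set.
- *The efficacy-reason inclusion should override every PPS criterion.* That would keep ineligible, wrongly dosed or poorly compliant patients and defeat the purpose of the set.

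**Impact is limited.** This stands. The PPS is secondary, the FAS is primary for efficacy, the primary endpoint is safety in the SAF, and section 7 plans no formal comparisons.

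**Conclusion.** The point holds in a limited form. Section 7.2.2 contains two rules that conflict for a patient who progresses, stops ELIGARD and has a listed drug recorded by the Early Withdrawal visit. If the medication exclusion is applied as written, observed progressors leave the PPS and its time-to-PSA-progression result becomes more favourable than that of the FAS. This weakens the PPS in the role that section 7.4 gives it.

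The direction rests on two assumptions: that listed-drug use is more frequent among progressors than among others, and that use after stopping counts as concomitant. The size cannot be derived from the protocol. No effect is shown on the FAS, the testosterone categories or the primary safety analysis. The conflict should be resolved before patients are allocated to analysis sets.

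**What to change.** In section 7.2.2, and in the Classification Specifications:

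1. Limit the prohibited-medication criterion to use that starts before documented PSA progression, CRPC or discontinuation of ELIGARD.
2. State that the inclusion of patients who stopped for efficacy-related reasons overrides this medication criterion only. The eligibility, dosing and compliance criteria stay as they are.
3. For patients kept in this way, do not use any PSA or testosterone value taken after the listed drug starts, other than one needed to confirm a progression already documented.

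The criterion for patients who met a withdrawal rule but were not withdrawn also stays. A man who adds a listed drug and simply continues in the study can still be excluded on that ground.

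The cost is a few sentences. Medication start dates are already collected (section 5.8.3). The PPS result may look slightly less favourable. The change concerns the analysis-set definition only, not which drugs are permitted or when patients are withdrawn.
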